3.3 Hypotheses and Objectives

The primary hypothesis is that one year feeding with pHF will be more efficacious than with eHF in the treatment of 6–12 month-old infants with IgE-mediated CMA.

Secondary hypotheses are that:

- 1. one year feed with pHF will be as safe as with eHF for 6-12 month-old infants with IgE-mediated CMA
- 2. one year feeding with pHF will be more efficacious than with eHF in inducing CM desensitisation for 6-12 months old *pHF-tolerant* infants with IgE-mediated CMA
- 3. one year feeding with pHF will be more efficacious than with eHF in inducing CM desensitisation for 6-12 months old *pHF-reactive* infants with IgE-mediated CMA
- 4. infants who cannot tolerate pHF at the start of the study, will be able to tolerate it after a short Oral Immunotherapy Treatment (OIT) regimen to pHF

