6.1.1 Visit 1 Inclusion Assessments

- 1. Infant aged 6 to 12 months, inclusive.
- 2. Convincing medical history of *IgE-mediated* allergic reaction following ingestion of cow's milk formula, as determined by trial physician.
- 3. Infant fed with formula, either exclusively or mixed with breastfeeding.
- 4. Weight of at least 7.5kg.
- 5. Written informed consent by parent/legal guardian prior to completing any study-related procedure.
- 6. Titre of cow's milk-specific IgE in serum, equal or higher to 2 kU/L (collected at visit 1, confirmed prior to visit 2/3), at inclusion **or** wheal reaction of equal or over 5mm to SPT* to CM at inclusion

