8.4.1.1 VISIT 1 (Screening Visit)

Visit 1 will last up to 2-3 hours. In this visit, each participant's eligibility will be checked against the **inclusion and exclusion criteria** (see sections 6.1.1 and 6.2.1). Evidence for the participant's eligibility will be collected and recorded in the patient's medical records.

Participants will undergo the following assessments:

- 1. Obtain informed consent: See section 8.3.
- Demographics & full medical history and diet: Date of birth, birth weight, gestation time, gender, parity, race, number of siblings, family history of allergic disease (eczema-atopic dermatitis, Allergic rhinoconjunctivitis, asthma, and food allergy) and other epidemiological characteristics. Details of any personal history of disease with focus on asthma, urticaria and angioedema, atopic dermatitis, food allergies, and drug allergies. Concomitant medication.
- 3. Physical Examination, current medical history & vital signs: Weight, length, EASI Score & history of wheeze. The following will be confirmed to be normal and a statement to this effect recorded in the medical notes: general physical examination with chest auscultation, Peripheral arterial pulse, heart rate, systolic and diastolic blood pressure, respiratory rate, and oxygen saturation.
- 4. Skin prick tests: will be conducted for cows' milk using whole, fresh milk, egg, House dust mite mix, cat dander, 6 grass pollen mix.
- 5. Blood sample for antigen-specific IgE to the following antigens: IgE levels to CM (CM-IgE), Alpha lactalbumin (ALA-IgE), beta lactoglobulin (BLG-IgE), and casein (Cas-IgE).
- 6. Safety blood tests: The following will be confirmed to be normal and a statement to this effect recorded in the medical notes:

- Haematology: Full blood count
- Biochemistry: Liver function tests; Urea; creatinine.
- 7. Collection of blood samples for storing: These will be collected only where **consent** has been provided and processed and stored locally until transferred to the central laboratory.

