8.9.1 Safety Assessments

• At each trial visit, the following will be confirmed to be normal: general physical examination with chest auscultation, Peripheral arterial pulse, heart rate, systolic and diastolic blood pressure, respiratory rate, and oxygen saturation. In case any abnormality is observed, any further actions, including continuation, should be based on clinical judgement and GCP.

- Haematology and biochemistry blood tests will be confirmed as normal at visit 1. In case any abnormality is observed, any further actions, including continuation, should be based on clinical judgement and GCP.
- Weight and height will be measured in kg and cm with locally available equipment and recorded in the participant's medical notes during all visits to assess development of the infants.

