11.2 Method of Randomisation

Participants will be equally randomised to eHF or pHF (1:1 ratio) using a secure (24-hour) web-based randomisation programme, controlled centrally by LCTC to ensure allocation concealment. Randomisation lists will be generated using block randomisation with random variable block length, stratified by site and initial tolerance to pHF. The lists will be produced by an independent statistician (who is not otherwise involved in the DREAM study) at LCTC.

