11.5 Analysis Plan

The trial will be analysed using the International Conference on Harmonisation E9 guidelines and reported using the 'Consolidation Standard of Reporting Trials' (CONSORT) guidelines.

The analyses of primary and secondary outcomes will use the principle of intention to treat, based on all the randomised participants, as far as is practically possible. A p-value of 0.05 or less will be used to declare statistical significance for all analyses and results will be presented with 95% confidence intervals. Baseline characteristics will be presented but no comparisons will be undertaken, rather the clinical importance of any imbalance will be noted.

Binary data (including the primary outcome of the proportion of patients who are no longer allergic to CM protein) will be reported in terms of relative risk and analysed using logistic regression, adjusted for the stratification factors (site and initial tolerance to pHF). There will be a secondary analysis of the primary outcome using a chi-squared test for consistency with the sample size calculation. There will also be two subgroup analyses of the primary outcome, the first will include patients who initially tolerate pHF and the second will include patients who did not initially tolerate pHF.

Continuous data will be presented as means and standard deviations and analysed using two-sample t-tests (if data is skewed, medians and ranges will be presented, and analysis will be by Mann Whitney U tests). All related AEs and serious adverse events SAEs reported by the clinical investigator will be presented, identified by treatment group, but no formal comparisons will be made across the treatment groups.

Missing data will be monitored, and strategies developed to minimise its occurrence, however as much data as possible will be collected about the reasons for missing data and this will be used to inform the handling of missing data.

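### Height and weight are to be compared by an unadjusted t-test although baseline values and the stratification factors are available, which gives a wider confidence interval than necessary

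*Protocol*

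**What the plan says.** Section 11.5 sets one rule for every continuous outcome: "Continuous data will be presented as means and standard deviations and analysed using two-sample t-tests". For skewed data it gives medians, ranges and Mann-Whitney U tests. Neither branch names a covariate. Height and weight are secondary outcomes 7 and 8 (section 3.4.2), so the rule applies to them.

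Binary outcomes are treated differently in the same section. They are to be "analysed using logistic regression, adjusted for the stratification factors (site and initial tolerance to pHF"), the two factors used in section 11.2, where randomisation is "stratified by site and initial tolerance to pHF".

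On baseline differences, 11.5 says: "Baseline characteristics will be presented but no comparisons will be undertaken, rather the clinical importance of any imbalance will be noted".

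The covariates exist. The visit 1 examination (8.4.1.1) records "Weight, length, EASI Score & history of wheeze", and section 8.5 requires baseline assessments to be complete before randomisation. Section 8.9.1 places growth under safety assessments: "Weight and height will be measured in kg and cm with locally available equipment". Section 3.3 gives the first secondary hypothesis: "one year feed with pHF will be as safe as with eHF for 6-12 month-old infants with IgE-mediated CMA". Section 11.1 states that the main features of the analyses are in the protocol, so the t-test is a stated choice and not a detail deferred to the SAP.

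**The concern.** Body size at about one year of follow-up depends strongly on body size at entry. The entry criterion is wide ("Infant aged 6 to 12 months, inclusive"), both sexes are pooled, and each site uses its own equipment. Much of the spread in length and weight at visit 8 is therefore predictable from the visit 1 value. An unadjusted t-test leaves that predictable part in the error term, and a chance difference in baseline length between the arms carries through into the estimate. If site or pHF tolerance predicts growth, ignoring the factors that stratified the randomisation also overstates the standard error.

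Adverse events will be listed by arm without formal comparison (11.5), so growth is one of the few safety-related measures that is formally compared. For a hypothesis that one formula is as safe as the other, what can be concluded depends on how narrow the interval is. The documents set no growth margin or growth power target and give no specific reason to expect a growth deficit, so only precision is at stake.

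**Working it through.** **The plan's own figure.** Section 11.3 gives 82 per group for 0.35 versus 0.60, two-sided 0.05, 90% power. With mean proportion 0.475:

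n = [1.960·√(2·0.475·0.525) + 1.2816·√(0.35·0.65 + 0.60·0.40)]² / 0.25² = (1.384 + 0.876)² / 0.0625 = 81.8, so 82 per group. Then 82/0.8 = 102.5, so 103 per group and 206 in total. Both figures reproduce. They concern the primary outcome; no precision is stated for growth. I use 82 per arm below.

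**Age at visit 8, from the protocol's windows** (6.1.1, 8.4.1.2, 8.4.1.3, 8.7.1.1, 8.7.4.1):
- Youngest: 6 months + 3 d + 2 d + 46 weeks = 6 months + 327 d = 16.7 months.
- Oldest: 12 months + 21 d + 6 weeks + 50 weeks = 12 months + 413 d = 25.6 months.
- Span 8.8 months at the extremes. With uniform entry age and the 7.5 kg weight floor, the SD is 1.7 months and the central 90% is about 18.5 to 24.0 months.

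**Growth inputs (assumptions, none in the protocol).**
- Length: SD within age and sex 2.4 cm at visit 1 and 2.7–3.0 cm at visit 8; growth 1.35 cm/month before 12 months and 0.85–1.0 after; sex difference 1.2–1.6 cm.
- Weight: boys' mean 7.4–7.9 kg at 6 months and 9.35 kg at 12 months; girls 0.65 kg less at visit 1 and 0.6 kg less at visit 8; SD 0.95 kg at visit 1 and 1.2 kg at visit 8; gain 0.18 kg/month.
- Weight–length correlation 0.6; visit 1 to visit 8 tracking correlation 0.6–0.8.
- The pHF-reactive share follows from section 11.3.1: 0.33/(0.33 + 0.67·0.5) = 0.496.

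Forty-eight combinations were simulated, with 400,000 infants each. The weight floor keeps 68–77% of them.

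**Half-widths.** Half-width = 1.975 · SD · √(2/82) = 0.3084 · SD.

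| Analysis | Length SD (cm) | Length half-width (cm) | Weight SD (kg) | Weight half-width (kg) |
|---|---|---|---|---|
| t-test on visit 8 value | 2.83–3.37 | 0.87–1.04 | 1.04–1.15 | 0.32–0.35 |
| t-test on change from visit 1 | 1.78–2.62 | 0.55–0.81 | 0.73–1.00 | 0.23–0.31 |
| ANCOVA on visit 1 value | 1.70–2.45 | 0.52–0.76 | 0.73–0.97 | 0.23–0.30 |

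Compared within each assumption set, ANCOVA is 23–44% narrower than the t-test on the visit 8 value for length, and 14–32% for weight. To match it for length, an unadjusted test needs about 82/(1−0.23)² = 138 to 82/(1−0.44)² ≈ 260 infants per arm. Compared with a t-test on change, ANCOVA is 2–10% narrower for length and 0–3% for weight. Adding age and sex after baseline length changes the half-width by less than 0.02 cm.

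**Chance imbalance.** Baseline length SD is 2.88–3.07 cm, so the standard error of the arm difference is 0.1562 · SD = 0.45–0.48 cm. The probability of a difference above 0.5 cm in either direction is 0.27–0.30. The slope of visit 8 on visit 1 length is 0.66–0.88, so a 0.5 cm baseline difference moves the unadjusted visit 8 difference by 0.33–0.44 cm.

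**Cross-check without growth assumptions.** For a baseline correlation r, ANCOVA multiplies the standard error by √(1−r²): 0.95 at r = 0.3, 0.87 at 0.5, 0.71 at 0.7, 0.60 at 0.8. The t-test standard error is thus 1/0.87 = 1.15 to 1/0.60 = 1.67 times larger for r of 0.5–0.8. A separate simulation with 164 infants, 12 sites and stratified blocks fitted baseline, 11 site terms and tolerance. At a difference of 0.44 SD, power rose from about 80% to 88% (r = 0.5), 97% (0.7) and 99.6% (0.8). Without the site and tolerance terms the formula gives 90%, 97.5% and 99.7%, so the extra parameters cost little.

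**The case against.** The strongest reply is that nothing here is invalid. A two-sample t-test is unbiased under randomisation, its interval already allows for chance baseline differences, and the protocol sets no growth margin against which a wider interval would fail. All of this is correct. The point is one of efficiency, and the imbalance figures illustrate the same loss; they are not a second harm.

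Section 11.5 is also generic. It names a test but neither a scale nor a visit. The SAP could derive z-scores, use visit 9 instead of visit 8, or analyse change from visit 1. Section 8.8.2 frames skin prick wheal and specific IgE as comparisons between visits 1 and 8. If growth were handled that way, most of the gain would already be realised. This stands as a condition on the size, and the change-score figures belong beside the headline ones. But the protocol says nothing of the kind for height or weight, and ANCOVA is essentially never less precise than either t-test.

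The growth inputs are assumed, and with a weak correlation (r = 0.3) the standard error falls by only 5%. That limits confidence in the centimetres but not in the direction. The age span and pooled sexes add nothing once baseline length is fitted. They matter because they make baseline length predictive. No document shows that site or pHF tolerance predicts growth, so no gain is claimed for those terms; the case for them is consistency with the randomisation and with the binary analysis.

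**Conclusion.** The concern holds. Section 11.5 fixes an unadjusted test for height and weight while a strong covariate is collected before randomisation and the same section adjusts binary outcomes for the stratification factors. If the visit 8 value is analysed, the interval for length is wider than needed by an amount that ANCOVA would cut by 23–44%, and for weight by 14–32%. If change from visit 1 is analysed, the remaining gain is 2–10% and 0–3%. These ranges rest on 82 evaluable infants per arm and on assumed growth SDs, velocities and tracking correlations of 0.6–0.8. There is no bias, and the primary outcome and sample size are untouched. The amendment is worth making because it costs almost nothing and the growth comparison bears on a safety hypothesis.

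**What to change.** In section 11.5, state that weight and length at visit 8 are analysed by linear regression on treatment, adjusted for the visit 1 value, site and initial pHF tolerance, and report the adjusted difference with its 95% confidence interval. Naming the visit also settles the choice between visits 8 and 9. The scale (raw or age- and sex-standardised) can stay with the SAP.

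The cost is one or two sentences. All data are already collected, so there are no new visits or measurements. The model gains about 13 parameters with 12 sites (baseline value, tolerance and 11 site terms). Small sites may need pooling or a random effect, and the rule for that should be fixed in advance.

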3.4 Outcome measures/endpoints

3.4.1 Primary Outcome/Endpoint

The primary outcome is whether the infant is characterised as CM protein-tolerant as per the result of a double-blind, placebo-controlled food challenge (DBPCFC) which will take place 12 months after randomisation (randomisation will take place at V4 for pHF-reactive infants and V3 for pHF-tolerant infants).

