3.4.2 Secondary Outcomes/Endpoints

- 1. The dose at which reactivity occurs in the DBPCFC
- 2. The maximal wheal size of skin prick test to cows' milk
- 3. Specific IgE levels to cows' milk, casein, a-lactalbumin and b-lactoglobulin
- 4. EASI scores for Eczema
- 5. Wheeze (during last 12 months, use of systemic steroids, hospitalisations)
- 6. Doctor diagnosis of other food allergies
- 7. Height
- 8. Weight
- 9. Adverse events from the visit where infants are put on the study product (V3 for 'pHF tolerant' and V4 for 'pHF-reactive' CMA infants) to the final visit (V9)

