10 SAFETY REPORTING

10.1 Time Period for Active Monitoring of Safety Events

The "active monitoring" of all safety events experienced by trial participants will be from randomisation until 48 hours after visit 9.

Any additional information on selected adverse events related to the initial challenges, will be captured in the Challenge Form (see sections 8.4.1.2 and 8.4.1.3). Expected adverse events during the challenges will not be included in the adverse events log, but rather in the challenge logs.

Any safety events occurring *after* the end the active monitoring period that meet the definition of **serious** (see section 10.3) must continue to be reported by sites to the LCTC in accordance with the timeframes and procedures described in section 10.9.

Upon becoming aware of a serious adverse event (SAE/Related SAE/RUSAE), the investigator or other delegated member of the site team must report this to the LCTC **within 24 hours**.

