10.2 Terms and Definitions

Table 1: Terms and Definitions of Safety Events

Adverse Event (AE)	Any untoward medical occurrence, unintended disease or injury or any untoward clinical signs (including an abnormal laboratory finding) in subjects, users, or other persons whether or not related to the investigational product.
Related Adverse	An AE which resulted from administration of any of the research procedures
Event (Related AE)	- i.e. assessed as "probably", "possibly" or "almost certainly" related to the
	trial procedures (see section 10.5).
Serious Adverse	An adverse event which meets the definition of "serious" (see section 10.3).
Event (SAE)	
Related Serious	An adverse event which meets the definition of "serious" (see section 10.3).
Adverse Event	A SAE which is assessed to be "probably", "possibly" or "almost certainly"
(Related SAE)	related to the trial procedures (see section 10.5).
Related Unexpected	A Related SAE which is not expected, i.e. not consistent with the known
Serious Adverse	effects of the trial procedures (see section 10.5).
Event (RUSAE)	

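### Section 11.5 plans to show by arm only related AEs and SAEs, although the declared safety outcome in 3.4.2 is all adverse events

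*Protocol*

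**What the plan says.** - **The outcome.** Section 3.4.2, item 9, opens "Adverse events from the visit where infants are put on the study product" and runs to the final visit, V9. It sets no condition on causality or seriousness.
- **The definition.** Section 10.2 counts an untoward occurrence as an AE "whether or not related to the investigational product". An AE is a related AE only if rated possibly, probably or almost certainly related. The two remaining ratings in section 10.5 are unlikely and unrelated.
- **The collection.** Sections 10.9.2 and 10.11 require every safety event to go on an AE form, whatever its seriousness, causality or expectedness. The exclusions in section 10.7 do not turn on the causality rating.
- **The presentation.** Section 11.5 states: "All related AEs and serious adverse events SAEs reported by the clinical investigator will be presented, identified by treatment group". It plans no formal test between the arms on these events, and it gives no time window.
- **The monitoring window.** Under section 10.1, active monitoring "will be from randomisation until 48 hours after visit 9".
- **The purpose.** Section 3.3.2 makes safety the first secondary objective. Section 3.3 adds the hypothesis that pHF feeding is as safe as eHF feeding.

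**The concern.** The outcome and its planned display do not cover the same events. Following 11.5 as written shows only part of outcome 9 by arm, and the part is chosen by a case-by-case causality judgement. Counting every event by randomised arm needs no such judgement, which is what makes it the more robust safety evidence in a randomised trial.

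The filter is a particular worry in this population. Table 4 lists urticaria, eczema exacerbation and acute bronchospasm among the expected events, and atopic infants also have these as background disease. The unlikely category in section 10.5 cites the participant's own clinical condition as an alternative explanation. An investigator acting in good faith can therefore rate a real formula effect as unlikely, and if it is not serious it leaves the by-arm display. What is at stake is the completeness of the evidence for the as-safe-as hypothesis. The absence of a formal test is a separate choice and is not the complaint.

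**Working it through.** The protocol attaches no number to the safety outcome, so there is no plan figure to reproduce. The main check is a comparison of the sections.

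**Step 1. Which events appear where**

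| Event | In outcome 9 (3.4.2) | Recorded (10.9.2, 10.11) | In by-arm display (11.5) |
|---|---|---|---|
| SAE, any causality | yes | yes | yes |
| Non-serious, possibly / probably / almost certainly related | yes | yes | yes |
| Non-serious, unlikely or unrelated | yes | yes | **no** |

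The last row is the gap.

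**Step 2. Is the gap covered elsewhere?** In part. EASI score (outcome 4) and wheeze episodes with related steroid use and hospitalisation (outcome 5) are recorded at all face-to-face visits under section 8.8.2, with no causality filter. Weight and height are outcomes too. Non-serious urticaria rated unlikely or unrelated has no other route. Section 10.12 sends an annual list of all safety events to the ethics committee and IDSMC, but does not say that it is by arm, and it is not the trial analysis.

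**Step 3. Illustrative size.** All inputs here are assumptions: formula-caused non-serious events in 10% of eHF and 30% of pHF infants, and a share m of them, equal in both arms because raters are blinded, rated unlikely or unrelated.

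Shown risk = true risk × (1 − m)

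| m | eHF shown | pHF shown | Difference | Ratio |
|---|---|---|---|---|
| 0 | 10% | 30% | 20 points | 3.0 |
| 0.30 | 0.10 × 0.70 = 7% | 0.30 × 0.70 = 21% | 14 points | 3.0 |
| 0.50 | 0.10 × 0.50 = 5% | 0.30 × 0.50 = 15% | 10 points | 3.0 |

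The absolute excess shrinks in proportion to m. The ratio does not move.

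**Step 4. Time windows.** Section 3.4.2 starts at V3 or V4. Section 3.4.1 says "randomisation will take place at V4 for pHF-reactive infants and V3 for pHF-tolerant infants", so 3.4.2 and 10.1 start at the same visit. They differ at the end: 3.4.2 stops at V9, while 10.1 adds 48 hours, the period of the follow-up contact for late symptoms in section 8.7.4.2.

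**The case against.** The strongest reply has four parts.

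1. **Section 11.5 gives main features only.** Section 11.1 says so and promises a separate analysis plan, and 11.5 does not contain the word *only*. This stands against one inference that a reader might draw: that non-serious unrelated events will never be shown by arm. The documents do not rule such a table out. It does not remove the mismatch, because 11.5 names a specific restricted set. An analysis plan that follows 11.5 omits part of outcome 9, and one that follows 3.4.2 goes beyond 11.5.
2. **Eczema and wheeze are captured without a filter.** This stands, and it narrows the gap to other non-serious events.
3. **The filter is loose and blinded.** Related includes possibly, which allows for a contribution from the infant's own condition. The treating investigator's opinion is never downgraded (10.5), and site teams are blinded (8.6). This makes differential misrating less likely and supports an unchanged ratio in Step 3. It does not prevent a real effect from being rated unlikely, nor the absolute excess from shrinking.
4. **The windows hardly differ.** This largely stands. A reader might infer that 11.5 uses a different window from 3.4.2, but 11.5 states none. A reader might also infer that the V3 cow's milk challenge reactions, which every randomised pHF-tolerant infant has, would swamp outcome 9. Section 10.1 sends expected challenge reactions to the challenge logs, and the schedule in section 7 marks no adverse event assessment at V3. The 48-hour difference at the end is small, and the follow-up contact is itself a listed V9 procedure.

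**Conclusion.** The mismatch in event set holds. Non-serious AEs rated unlikely or unrelated are part of the declared safety outcome and are recorded, but they lie outside the by-arm presentation that 11.5 describes. For a trial with an as-safe-as hypothesis this is worth correcting.

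The size cannot be derived from the protocol. On the assumed 10% and 30% rates, a visible excess of 14 or 10 points instead of 20 corresponds to misrated shares of 30% and 50%, and the risk ratio stays at 3.0 if misrating is equal in both arms. If few events are misrated, little is lost. The window difference between 3.4.2 and 10.1 is a minor alignment point and carries no weight in this conclusion.

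**What to change.** - **Section 11.5:** replace the restricted set with: *All AEs, and separately related AEs and SAEs, will be presented by treatment group.* The decision not to test formally can stay.
- **Section 3.4.2, item 9 (minor):** use the window of section 10.1, from randomisation to 48 hours after V9, with initial-challenge reactions kept in the challenge logs as 10.1 already provides for the expected ones.

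The cost is a wording change and one extra table. No new data are needed, since AEs are already recorded regardless of causality, and nothing in the management of participants changes.
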